 Including: total cholesterol, triglycerides, HDL and LDL

 Including: hemoglobin, hematocrit, red blood cell (RBC) and RBC morphology, white blood cell (WBC) and differential WBC count, platelet count, mean corpuscular volume (MCV), mean corpuscular hemoglobin concentration (MCHC).

 Serum biomarkers – CK-18, LPS, adiponectin, GLP-1 and cytokines (IL-1 $\alpha$ , IL1 $\beta$ , IL-2, IL-3, IL-4, IL-6, IL-10, IL-13, IL-12, IL-17 $\alpha$ , IL-23, IFN $\gamma$ , TGF- $\beta$  and TNF $\alpha$ )

 PBMC - FACS analysis for CD4 CD8 CD25 FoxP3 NKT CD62 CD69 T cells

 Serology (including HIV, HCV and HBV test) results will be acceptable for eligibility within range of 6 months prior to screening.

 MRI: Baseline MRI to be performed as soon as subject eligibility is determined. Week 24 MRI to be done within +/- 2 weeks week 24.

 Randomization is to be done within 2 weeks post baseline MRI, when the MRI result is available for stratification (hepatic fat fraction form – to be received by central imaging lab).

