### 7.2.9 **Week 24 (or early withdrawal from treatment)**

All subjects will return to the clinic and the following procedures performed and documented

- A targeted physical examination (see [Section 7.3.2](#))
- AE assessment (see [Section 10.2](#))
- Vital signs (blood pressure, temperature, heart rate and respiratory rate) (see [Section 7.3.3](#))
- Measurement of bodyweight and waist and hip circumferences (see [Section 7.3.3](#))
- Concurrent medication recording (see [Section 9](#))
- Study medication accountability (return of all unused medication) (see [Section 8](#))
- Diet and exercise counseling and 7-day diary issue (see [Section 7.3.5](#))
- Administration of the AUDIT questionnaire
- MRI scan (see [Section 7.3.13](#))
- Urine pregnancy test for women of childbearing potential (see [Section 7.3.10](#))
- Collection of blood and serum samples for:
  - Hematology (see [Section 7.3.6](#))
  - Coagulation (see [Section 7.3.6](#))
  - Fasting clinical chemistry (see [Section 7.3.6](#))
  - Fasting lipid analysis, including HOMA-IR (see [Section 7.3.6](#))
  - HBA1C
  - Pharmacokinetics (see [Section 7.3.8](#))
  - PBMCs (see [Section 7.3.9](#)) – at selected sites only
  - Biomarker analysis including CK-18 fragments, LPS, adiponectin, GLP-1 and cytokines (see [Section 7.3.9](#))
  - Serum metabolomics
- Collection of a stool sample for microbiome assessment (see [Section 7.3.11](#)) – selected sites only.

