### 11.3 Withdrawal of Subjects from Study drug

[Section 10.6](#) provides guidance for dose discontinuation of Study drug in the event of AEs or abnormal laboratory values. If a subject permanently discontinues study drug, for example as a result of an AE, subjects should be encouraged to continue participation in the study in order to obtain ongoing measurement of study outcomes to minimize missing data. At a minimum, every attempt should be made to continue to follow the subject until resolution of the adverse event. All subjects who discontinue study medication dosing should be followed for at least 28 days after the last dose of Study drug in order to monitor subjects for possible post-treatment events which may occur after Study drug has been discontinued.

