In the case of multiple occurrences of the same visit, the data from the latest visit date will be used if prior to the first dose. After the first dose, the data from the earliest visit date will be used. All data collected will be presented in the data listings.

All programming for statistical analysis, data listing and production of figures will be done in version 9.4 of SAS.

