7.2 Primary efficacy analyses

The hepatic fat fraction will be summarised and tabulated for the Baseline and Week 24 visits along with change from Baseline by randomised treatment group. Change in hepatic fat fraction from Baseline will be analysed using analysis of variance on the ITT, PP and FAS populations, where the model will include the treatment group and another subgrouping variable. As determined by baseline values, hepatic fat fraction categories ($\leq 10\%$, $>10\% - <21\%$, $\geq 21\% - <30\%$ and $\geq 30\%$), HbA1c group ($< 6\%$ and $\geq 6\%$), and ALT (greater or less than 1.5 x the upper normal limit) will be used to subgroup the analysis populations. Further, data from liver biopsies up to 6 months prior to screening will also be used to subgroup analysis populations based on fibrosis (0-1 vs. 2-3), NAS inflammation (0-1 vs. 2-3), and NAS ballooning (0-1 vs. 2). These will be used in addition to the main effects factors and the two-way interaction of those main effects.

In the primary analysis, any missing data will remain missing. Treatment effects between placebo and each of the active treatment groups within each of the hepatic fat and HbA1c categories will be generated and tested for significant differences between treatment and placebo using pre-specified contrasts.

To examine the effect of treatment within the various levels of these subgroup variables, a mixed models ANOVA will be employed if there are an appropriate number of observations in each cell (created by the crossing of study treatment and subgroup categories) and the data does not differ significantly from a normal distribution. In the event that this is not the case, the data will be ranked in an attempt to normalise it, and pairwise contrasts between treatment groups will be performed using Wilcoxon rank sum tests within each combination of visit and subgroup variable level will be performed. However, if the ranked data is also not normally distributed, a permutation test will be employed whereby the unranked data will be randomly sampled (Lehmann, 2006). No adjustment for multiple testing will be made. See Appendix 1 for more information on both the Wilcoxon rank-sum test and the permutation test.

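### Early-withdrawal MRIs share the Week 24 visit, and the SAP's keep-the-earliest rule, read literally, lets a mistimed scan stand as the Week 24 primary outcome in FAS and ITT

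*SAP*

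**What the plan says.** **Protocol, Table 1 and 7.2.9.** The schedule has a single column, W24/WD. Liver MRI is marked there and at Baseline only. Section 7.2.9, headed "Week 24 (or early withdrawal from treatment"), gives one procedure list for both situations. It includes the MRI and sets no minimum time on treatment.

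**Protocol 11.3.** For subjects who permanently stop study drug: "subjects should be encouraged to continue participation in the study in order to obtain ongoing measurement of study outcomes to minimize missing data".

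**SAP 3.3.** The duplicate rule begins "In the case of multiple occurrences of the same visit". Before the first dose the latest record is kept. Afterwards: "After the first dose, the data from the earliest visit date will be used". Neither the MRI nor any other efficacy measure is exempted.

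**Timing windows.** Table 1, footnote 7: "Week 24 MRI to be done within +/- 2 weeks week 24". SAP 3.2 sets ±3 days for all visits after the first four weeks. Neither text says what happens in the analysis to a scan outside its window.

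**Missing data.** SAP 7.2: "In the primary analysis, any missing data will remain missing". Multiple imputation is a sensitivity analysis only (SAP 3.3 and 7.2).

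**The concern.** The primary outcome is change in hepatic fat fraction at Week 24. A subject who stops drug at, say, Week 6 is scanned then under the visit label that also carries the primary endpoint. If that subject stays on study and is scanned again at Week 24, the duplicate rule applied as written keeps the Week 6 scan and discards the one that Protocol 11.3 tries to secure. If there is no second scan, nothing in the SAP prevents the Week 6 value from being counted as Week 24.

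In either case the analysis would mix follow-up times while reporting a Week 24 effect. The multiple imputation would also take the early value as observed, so the sensitivity analysis intended to examine missing outcomes would not touch these subjects.

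**Working it through.** **1. How a scan could reach the Week 24 analysis**

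| Situation | Text that applies | Result in FAS and ITT |
|---|---|---|
| Withdrawal scan, then a scan at Week 24 | SAP 3.3 duplicate rule, if both are recorded as W24/WD | Withdrawal scan kept, Week 24 scan dropped |
| Withdrawal scan only | No assignment rule; SAP 3.2 and Table 1 footnote 7 do not say they govern analysis | Could be counted as Week 24 or set to missing; not specified |
| Completes 24 weeks, one scan | No conflict | Week 24 scan used |

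The PP set requires completion of the 24-week treatment period (SAP 3.1), so early withdrawals are not in it.

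**2. The two windows**

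Baseline is Day 0, so Week 24 is Day 24 × 7 = 168. Footnote 7 allows the MRI from Day 154 to Day 182. SAP 3.2 allows Day 165 to Day 171. If the SAP window were used as an analysis window, it would remove early scans, but also MRIs that the protocol permits.

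**3. The plan's own power figure**

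Inputs (Protocol 12.1): 40 per arm, difference 5 points, SD 7.3, two-sided α 0.05, unpaired t-test. SD check: √(36 + 36 − 2 × 0.25 × 36) = √54 = 7.35, against 7.3 stated. Power by the noncentral t distribution with 78 df is 85.7% at SD 7.3 and 85.2% at SD 7.35. The stated figure of about 85% is reproduced.

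**4. Attenuation (illustration)**

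The documents give neither a withdrawal rate nor a time course, so both are assumed. Let w be the share of Week 24 values that are early scans, and g the share of the full effect present at those scans. With no change on placebo:

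difference = 5 × [1 − w(1 − g)]

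If the effect builds linearly and withdrawals are uniform over 24 weeks, g averages 0.5. The range column uses g = 0 to 0.75.

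| w | Difference, g = 0.5 | Range, g = 0 to 0.75 |
|---|---|---|
| 10% | 4.75 | 4.50 to 4.875 |
| 20% | 4.50 | 4.00 to 4.75 |
| 30% | 4.25 | 3.50 to 4.625 |

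**5. Would the fix recover power?**

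Noncentral t, SD 7.3, g = 0.5 where early scans are counted; full 5-point effect where they are left missing in both arms:

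| w | Early scans counted (40 per arm) | Early scans missing (n per arm) |
|---|---|---|
| 10% | 82.0% | 81.7% (36) |
| 20% | 77.7% | 76.9% (32) |
| 30% | 73.0% | 71.1% (28) |

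Power is about the same, and slightly lower with the scans left missing.

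Protocol 11.5 also provides for replacing withdrawals until the planned number of completers is reached. With 40 completers per arm plus the early scans, n = 40/(1 − w), and the signal relative to the plan is (1 − w/2)/√(1 − w) = 1.001, 1.006 and 1.016 at 10, 20 and 30%. In that case counting early scans costs no power under this model. The attenuation of the estimate remains.

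**The case against.** The strongest reply is that the rule may never fire. A shared column and heading list procedures; they do not show that a withdrawal scan is recorded in the database as the Week 24 visit. SAP 3.1 defines the Early Termination population as subjects who withdrew before completing the Week 24 visit, and SAP 8.6 looks at their last available assessments separately. On that reading a withdrawal visit is not a Week 24 visit, and a Week 6 scan meets neither timing window. This stands as a reason for calling the misassignment possible rather than certain. It does not close the gap: the Early Termination group is a subset of the Safety population and does not govern how an MRI is assigned in FAS or ITT, and neither window is stated to do so.

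The two-scan route is also narrow. It needs a subject who stops drug, is scanned, stays on study and is scanned again. Protocol 11.3 only encourages staying, and Protocol 5.4 and 7.2.10 provide a follow-up about four weeks after stopping. That stands too; no retention rate is given.

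A reader might infer three stronger things that the documents do not support:

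- **That early scans certainly dilute the effect.** This holds only if the effect builds over time, and no time course is given.
- **That the defect costs the trial power which the fix would restore.** The comparison above shows otherwise.
- **That withdrawals are concealed.** They are tabulated by reason (SAP 4.2), shown in the disposition flow chart (SAP 4.1) and examined in the Early Termination analysis. What could go unseen is only that their Week 24 fat fraction is not a Week 24 measurement.

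**Conclusion.** The point holds as a gap in the analysis rules for the primary endpoint. The combined visit and the keep-the-earliest rule, read literally, select a withdrawal scan over a true Week 24 scan. For a lone withdrawal scan there is no assignment rule at all, and the two windows that might supply one disagree (±3 days against ±14 days). The exposure is in FAS and ITT, not PP.

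The consequence is a mistimed endpoint, and an early value taken as observed in the imputation analysis. The size cannot be fixed from the documents. Under linear build-up and uniform withdrawal, a 5-point effect would be estimated as 4.75, 4.5 or 4.25 points at 10, 20 or 30% early scans, assuming that every early scan is counted. The case for acting is the timing of the primary endpoint, not power. Because the change is cheap and touches the primary outcome, it should be made.

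**What to change.** In SAP 7.2:

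- Define the Week 24 hepatic fat fraction as the MRI within Day 168 ±14 days, which is the protocol's own MRI window, and state that this window governs the analysis. Reconcile SAP 3.2 with it.
- If several scans fall in the window, use the one nearest Day 168.
- Exempt the MRI from the earliest-record rule in SAP 3.3.
- Treat scans outside the window as missing at Week 24 in the primary analysis, and list them. Using them as auxiliary values in the multiple imputation is optional.

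Recording withdrawal and Week 24 visits under separate codes would make the rule easy to apply. The wording should be settled before unblinding, because a later choice between scans could be driven by the data.

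The cost is a few sentences in the SAP and possibly a few more missing outcomes. The primary analysis does not impute, so it would lose those subjects; only the sensitivity analysis would cover them.

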3.4 Data handling

Data collected during the course of this study have been entered into an IBM Clinical Development formerly known as eClinical OS (eCOS) electronic clinical record database, which is a commercially available database (Merge, now an IBM company) specifically designed for such use. Data is entered into the database at each study centre. SAS datasets are one of the outputs of the database. Following review, validation and correction of the data entered into the database, a meeting will be held to declare the file to be clean and proceed to data lock, after which no changes to the data are possible. At the Clean File meeting, analysis populations will be discussed and finalised. Following the signing of the Clean File document by all signatories, the randomisation code will be broken following Datapharm Australia standard operating procedures set for that activity.

4. SUBJECT DISPOSITION AND WITHDRAWAL

4.1 Subject disposition

Subject disposition will be presented in the form of a flow chart for the Clean File meeting which will be included in the study report. Information included in the flow chart will include the number of subjects enrolled, number available for each of the analysis populations (Safety, ET, ITT, FAS, PP) and reasons for those not available. The flow chart will include unblinded subject identification numbers. A summary table will be produced that provides counts and percentages of subjects in each analysis population and the reason for exclusion from subsequent analysis populations.

4.2 Study completion and withdrawal

A table will be produced that summarises the number of subjects enrolled, and number withdrawn by withdrawal reason.

5. DEMOGRAPHIC AND OTHER CHARACTERISTICS AT BASELINE

5.1 Demographic data

Demographic data collected at subject entry into the study, including age, gender, height, weight, BMI and race together with other characteristics recorded in the CRF at the Screening or Baseline visit will be summarised by descriptive statistics or frequency tabulations by treatment group. For the demographics and other data in this section, the FAS population will be used and grouped by treatment. Further tables will also be produced, which group the data by treatment, HFF and A1c levels.

5.2 Disease characteristics

Previous treatment regimens for NAFLD and NASH will be summarised by their current status and treatment group. Liver biopsy data collected prior to enrolment in the study will also be summarised, including fibrosis, inflammation, ballooning, and steatosis scores. Baseline clinical chemistry values such as ALT, AST and A_{1c} will also be presented. These characteristics may be used to subgroup populations in the primary analysis (as described in Section 7.2).

5.3 Medical history

Medical history entries will be coded using MedDRA. The data will be summarised and tabulated by SOC and Preferred Term as well as treatment group. The summary table will indicate resolved versus current events as collected in the eCRF.

5.4 Prior medications

Prior medications are those medications taken by subjects and ceased prior to entry into the study. These medications will be coded using WHO DD and will be summarised and tabulated by first and second level terms and treatment group.

5.5 Concomitant medications

Concomitant medications are those medications taken by subjects during the course of the study. These medications will be coded using WHO DD and will be summarised and tabulated by first and second level terms and treatment group. New medications are those drugs commenced during the study, and will be coded and presented in the same manner as concomitant medications.

5.6 Other data collected at Baseline

12-lead electrocardiographic values will be summarised and tabulated by treatment group. Summary tables for HbA_{1c} and hepatic fat fraction, including number of subjects in each category will also be produced.

6. COMPLIANCE

Compliance is derived from the drug accountability data and is calculated as the percentage of study treatment to be received versus that was actually taken by the subject. A table of compliance by treatment group will be produced, whereby counts of subjects that were <50%, 50%-<85%, 85%-115%, and >115% will be displayed. In cases where bottles were not returned and drug counts are not available, compliance for that period will be estimated from the eCRF compliance assessment according to the rules set within the Clean File document.

7. EFFICACY ANALYSES

7.1 Primary efficacy assessments

The primary outcome for this study will be the mean change from Baseline in the percentage fat content (hepatic fat fraction) of the liver measured by Magnetic Resonance Imaging (MRI) at Week 24.

7.2 Primary efficacy analyses

The hepatic fat fraction will be summarised and tabulated for the Baseline and Week 24 visits along with change from Baseline by randomised treatment group. Change in hepatic fat fraction from Baseline will be analysed using analysis of variance on the ITT, PP and FAS populations, where the model will include the treatment group and another subgrouping variable. As determined by baseline values, hepatic fat fraction categories ($\leq 10\%$, $>10\% - <21\%$, $\geq 21\% - <30\%$ and $\geq 30\%$), HbA1c group ($< 6\%$ and $\geq 6\%$), and ALT (greater or less than 1.5 x the upper normal limit) will be used to subgroup the analysis populations. Further, data from liver biopsies up to 6 months prior to screening will also be used to subgroup analysis populations based on fibrosis (0-1 vs. 2-3), NAS inflammation (0-1 vs. 2-3), and NAS ballooning (0-1 vs. 2). These will be used in addition to the main effects factors and the two-way interaction of those main effects.

In the primary analysis, any missing data will remain missing. Treatment effects between placebo and each of the active treatment groups within each of the hepatic fat and HbA1c categories will be generated and tested for significant differences between treatment and placebo using pre-specified contrasts.

To examine the effect of treatment within the various levels of these subgroup variables, a mixed models ANOVA will be employed if there are an appropriate number of observations in each cell (created by the crossing of study treatment and subgroup categories) and the data does not differ significantly from a normal distribution. In the event that this is not the case, the data will be ranked in an attempt to normalise it, and pairwise contrasts between treatment groups will be performed using Wilcoxon rank sum tests within each combination of visit and subgroup variable level will be performed. However, if the ranked data is also not normally distributed, a permutation test will be employed whereby the unranked data will be randomly sampled (Lehmann, 2006). No adjustment for multiple testing will be made. See Appendix 1 for more information on both the Wilcoxon rank-sum test and the permutation test.

Sensitivity analyses will be performed in the final study analysis and will use the same analysis method on the FAS and PP populations using the multiple imputation and analysis method to impute missing values and, finally, an analysis using the full set of ITT population data, but including study centre as an additional main effect.

Interaction effects with study centre will not be investigated. If any outliers are detected (defined as greater than ± 2 SD away from the mean for that group and visit combination), sensitivity analyses will be performed where those outliers are removed and then will be compared with the analysis where those outliers were not taken out.

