
Sample size determination:
	
Fat Liver Content Change from Baseline:                  The current sample size of 40 subjects per group should yield approximately 85% power to detect a treatment effect of at least -5% with respect to the difference in the mean change from Baseline between one of the IMM-124E treatment groups and placebo assuming a standard deviation (SD) of 7.3% (<math>\alpha=0.05</math>; two-tailed; unpaired t-test). The SD of 7.3% for the change from Baseline endpoint was derived assuming 1) SDs of 6% for each timepoint, 2) equal variances in each treatment group and 3) a low to moderate correlation of 0.25 between pre- and post-Baseline measurements.
 
Sample size and power estimates have not been adjusted for multiple comparisons or multiple endpoints, dropouts or stratification.
 
The analysis of each primary endpoint will be based on a linear model that incorporates the baseline measure as a covariate, the stratification factor and randomized treatment group. Pairwise comparisons of each active treatment group to control will be conducted via linear contrasts.

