Serum lipid profile values of total cholesterol, triglycerides and high and low density lipoproteins with change from Baseline and number of clinically significant values will be summarised and tabulated by visit and treatment group. Liver function values of ALT, AST, GGT, bilirubin and albumin, with change from Baseline will be summarised and tabulated by visit and treatment group. These liver function tests will also be correlated with HFF, CRP, and A1c. The proportion of subjects with ALT within the normal reference range at Week 24 will be summarised and tabulated by treatment group. Logistic regression modelling will be used to compare proportions in the Placebo group against each of the IMM-124E treatment dose groups using the same model used in the primary efficacy analysis, although the Baseline value of the liver function analyte will be used as a covariate. The area under the curve for change

from Baseline to Week 24, using the Baseline value as reference, for liver enzymes ALT, AST and GGT will also be analysed. For patients in the FAS population who withdraw prior to Week 24, the area under the curve will be adjusted in a manner comparable to a full 24 week period value.

The proportion of subjects demonstrating a decrease in liver percent fat at 24 weeks compared to baseline of 5%, 10%, 20% and 30% respectively will also be analysed. In a similar manner, proportional decreases in ALT, AST and A1c will be assessed using appropriate percentages.

Correlations between change in hepatic fat fraction and changes in ALT, C-reactive protein and A_{1c} will also be calculated.

The Fibrosis-4 Score will be calculated at each visit for which there is data. The formula is $FIB-4 = (Age * AST) / (Platelets / \sqrt{ALT})$. This score will be summarised and tabulated in the same manner as the primary endpoint.

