	Shift table of serum biochemistry by visit (Safety population)
	Haematology by visit (Safety population)
	Shift table of haematology by visit (Safety population)
	Vital signs by visit (Safety population)
	Physical examination results by visit

Figure Section	Figure Title (Population)
Section 11.4	
Difference in hepatic fat between Placebo and each dose level of IMM-124E (ITT, PP, FAS populations)
 
Difference in hepatic fat between Placebo and each dose level of IMM-124E by hepatic fat category and HbA1c (ITT, PP, FAS populations) (lattice graph)
 
Difference in hepatic fat between Placebo and each dose level of IMM-124E (ITT, PP, FAS populations with MI imputation where appropriate)
 
Difference in hepatic fat between Placebo and each dose level of IMM-124E by hepatic fat category and HbA1c (ITT, PP, FAS populations with MI imputation where appropriate) (lattice graph)
 
Proportion of subjects with normal ALT by visit (ITT, PP, FAS populations)
 
MELD score by visit (ITT, PP, FAS populations)
 
Proportion of subjects with 5% reduction of hepatic fat from baseline (ITT, PP, FAS populations)
 
Proportion of subjects with 10% reduction of hepatic fat from baseline (ITT, PP, FAS populations)
 
Body mass index, waist circumference and waist:hip ratio by visit (ITT, PP, FAS populations)
 
HbA1c by visit (ITT, PP, FAS populations)
 
HOMA-IR by visit (ITT, PP, FAS populations)
 
AUDIT results by visit (ITT, PP, FAS populations)

Section 12.2	Odds ratios of most common Preferred Terms (Safety population)

Sample Tables

Primary analysis

										Group comparisons					
Treatment	Visit / Value	n	Mean	SD	Median	Quartiles 1 & 3	Min	Max	Prob = 0	Normality Prob	Change	Ranks Prob	Ranks	Permut ations	Disp- arity
Treatment 1	Screening														
	Baseline														
	Timepoint 1														
	Change to Timepoint 1														
	Adj change to Timepoint 1 Difference from Treatment 2														
	Difference from Treatment 3														
	Change to Timepoint 2...														

Primary analysis with Subgrouping

Subgroup (e.g. HFF, A1c, ALT, Fibrosis, Inflammation, ballooning)	Treatment	Visit / Value	n	Mean	SD	Median	Quartiles 1 & 3	Min	Max	Prob = 0	Group comparisons					Disparity	
											Normality Prob	Change	Ranks Prob	Ranks	Permutations		
Group 1	Treatment 1	Screening															
		Baseline															
		Timepoint 1															
		Change to Timepoint 1															

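### SAP 7.2 departs, unflagged, from the protocol's baseline-adjusted primary model and does not say how the overall dose-versus-placebo comparison is adjusted

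*SAP*

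**What the plan says.** **Protocol.** The sample-size entry of the synopsis says the primary analysis will be "based on a linear model that incorporates the baseline measure as a covariate, the stratification factor and randomized treatment group". It adds: "Pairwise comparisons of each active treatment group to control will be conducted via linear contrasts". Section 12.2.1 names the FAS, in its heading, as the set for the primary assessment of efficacy. Section 8.1 stratifies allocation by baseline HFF (cuts at 10, 20 and 30%, with exactly 20% in the lower group) and by HbA1c (up to 6.0 versus above 6.0).

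**SAP 7.2.** Change in HFF is "analysed using analysis of variance on the ITT, PP and FAS populations, where the model will include the treatment group and another subgrouping variable". Six candidate variables follow: HFF category, HbA1c, ALT, fibrosis, inflammation and ballooning. The HFF cut is at 21% rather than 20%, and HbA1c is split as below 6 versus 6 and above. On model terms, the text says: "These will be used in addition to the main effects factors and the two-way interaction of those main effects". On contrasts: "Treatment effects between placebo and each of the active treatment groups within each of the hepatic fat and HbA1c categories will be generated".

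**Elsewhere in the SAP.** Section 7.3 uses the primary model for a logistic analysis, "although the Baseline value of the liver function analyte will be used as a covariate". Section 12 lists an unstratified analysis of change in HFF for each population, an overall figure, and a primary-analysis shell with the row "Adj change to Timepoint 1 Difference from Treatment 2". A separate shell is headed "Primary analysis with Subgrouping". Section 1 expands Adj as adjusted. Section 2.2 gives a reason for comparing doses within HFF strata: differential response seen in earlier NASH studies. Section 3.1 tests the ITT population only if a randomised subject was never dosed. Section 10 leaves changes from the protocol to the study report.

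**The concern.** The SAP changes the protocol's primary model without saying so, and the replacement is not fully specified. A programmer filling in the primary-analysis shell could fit treatment with HFF category, treatment with HbA1c group, or a model with an interaction, and could defend each from section 7.2. These fits have different precision, and the choice would be made outside the plan.

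Dropping the measured baseline also gives up precision. Baseline HFF is collected on everyone and, on the protocol's own correlation of 0.25, is strongly related to the change score. Allocation is stratified on it as well, so an analysis that ignores it reports a standard error that is too large. Finally, the only contrasts that section 7.2 pre-specifies are within categories, and the sample-size calculation does not describe their power.

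**Working it through.** **Inputs** (protocol 12.1): SD 6 at each timepoint, pre/post correlation r = 0.25, difference 5, 40 per arm, two-sided alpha 0.05, unpaired t-test, stated power about 85%. I also show r = 0.5. Power is from the noncentral t distribution.

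**1. The plan's own figure.** SD of change = 6 × √(2(1 − r)) = 6 × √1.5 = 7.35 (stated as 7.3). Power is 85.7% with SD 7.3 and 85.2% with 7.35. The stated figure reproduces, and it is the power of an unadjusted comparison of change.

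**2. Continuous baseline as covariate.** Residual SD = 6 × √(1 − r²) = 6 × √0.9375 = 5.81. The variance ratio is 33.75 / 54.0 = 0.625, a saving of 37.5%. The standard error of the difference is 5.81 × √(2/40) = 1.30, against 7.35 × √(2/40) = 1.64.

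**3. HFF category as a main effect.** The documents give no baseline distribution, so I assume a normal one with SD 6 and mean 15 to 22. With the SAP's cuts at 10, 21 and 30, the residual SD is 6.12 to 6.19 at r = 0.25.

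| Model for the overall contrast | Power, r = 0.25 | Power, r = 0.5 |
|---|---|---|
| Unadjusted change | 85.2% | 95.7% |
| HFF category as main effect | about 95% | about 98% |
| Continuous baseline HFF | 96.7% | 98.9% |

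A subgrouping variable unrelated to change in HFF (an assumption, for example ALT group) would leave power at about 85%.

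**4. Type I error under stratified allocation.** Stratifying by HFF makes the arms more alike at baseline than chance would, but an unadjusted test still counts the baseline variation in its standard error. I simulated three arms of 40 with permuted blocks within HFF strata. Assumed: baseline mean 18 to 22, block size 3 or 6, HbA1c split 50/50. The true type I error of a wholly unadjusted test is about 2 to 3%. With continuous baseline plus strata it is about 5%.

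**5. Within-category contrasts.** Difference 5, r = 0.25, 2n − 2 degrees of freedom. The documents give no category sizes, so these are assumed. HbA1c groups keep the full SD of change. HFF categories have less spread, about 6.15.

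| Assumed size per arm | HbA1c group (SD 7.35) | HFF category (SD 6.15) |
|---|---|---|
| 6 | 18.7% | 24.7% |
| 10 | 30.2% | 40.6% |
| 20 | 55.5% | 70.7% |

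**The case against.** The protocol sentence is a modest benchmark. It appears only in the synopsis, does not use the word continuous, and still refers to each primary endpoint and a single stratification factor, although the protocol now has one primary efficacy endpoint and two strata. Protocol 12 and 12.4 leave detail, including the use of covariates, to the SAP. The SAP coarsens baseline HFF rather than removing it. If HFF category is the term meant, most of the gain is kept: about 95% against 96.7%. The baseline remark in SAP 7.3 concerns a logistic model for ALT and could mean swapping in the relevant analyte, so it supports the absence of a covariate in the primary model without proving it. The trial is also declared exploratory. All of this stands, and it limits the weight of the point. It does not say which term goes into the overall model, and exploratory status does not define the primary estimate.

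Four stronger readings are tempting, and the documents do not support them.

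- **The SAP has no overall comparison.** It has a table, a figure and a shell for one, and Appendix 1 gives a rank test stratified by HFF category. What is missing is the definition of the adjustment.
- **The primary population is undefined.** The SAP ranks none of ITT, PP and FAS, but protocol 12.2.1 names the FAS and ITT is conditional. The open choice is mainly FAS versus PP.
- **The within-HFF contrasts are arbitrary.** SAP 2.2 gives a reason for them. It does so when describing the interim analysis, and it defines no unstratified contrast.
- **The interaction term forces an equally weighted average over categories, with much lower power.** The SAP proposes no such weighting.

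**Conclusion.** The point holds as a specification gap worth fixing. Section 7.2 departs from the protocol's primary model without flagging it, uses categories that do not match the randomisation strata, pre-specifies only within-category contrasts, and leaves the adjustment of the overall comparison open.

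The size is moderate. At the protocol's correlation, the readings run from about 85% to 97% power, and the spread narrows to 96% to 99% at r = 0.5. A reader might infer that the trial is underpowered or that false positives are inflated. Neither follows: an unadjusted analysis keeps at least the planned power, and under stratified allocation it is conservative. The type I error result applies only to a wholly unadjusted test and rests on the assumed baseline distribution, block size and HbA1c split. The within-category figures depend on assumed sizes, but all lie well below 85%, so the planned power should not be read as covering those contrasts.

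**What to change.** In SAP 7.2, define the primary analysis as Week 24 change in HFF regressed on treatment, continuous baseline HFF and the two randomisation strata, without interaction, in the FAS, with one overall contrast per dose against placebo. Use the strata as applied at randomisation: HFF cuts at 10, 20 and 30%, and HbA1c up to 6.0 versus above. The protocol synopsis also counts a diagnosis of type II diabetes towards the diabetic stratum, so state which rule was used. Tie the primary-analysis shell, the unstratified table and the overall figure to this model, and record the reason for any remaining difference from the protocol.

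Keep the within-category contrasts, with the rationale from SAP 2.2, as pre-specified secondary or exploratory analyses. Label the PP run, and the ITT run if triggered, as supportive.

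The cost is SAP wording only, since baseline HFF and the strata are already collected. The one downside is that within-category results lose primary status.
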